4.5. Study Day and Study Week

Study days will be numbered relative to the earliest date an ABS eMDPI device was dispensed (ie, ... -2, -1, 1, 2, ...). Day 1 is defined as the earliest date an ABS eMDPI device was dispensed and Day -1 is the day before the first ABS eMDPI device was dispensed.

Week I is defined as study day $(j + 1)$ to study day $(j + 7)$, inclusive where $I = 1$ to 12 and $j = 0, 7, 14, 21, 28, 35, 42, 49, 56, 63, 70, 77, 84$, respectively.

4.6. Handling Withdrawals and Missing Data

Any data that was collected prior a patient's withdrawal from the study will be used for analysis and presented in the data listings.

The following imputation rules will be used;

- If the return date of the last ABS eMDPI device returned is missing the patient's last date of contact or study completion date will be used as the return date (see Section 4.4 and Section 10.2).
- Adverse events or serious adverse events with missing start dates will be considered treatment emergent (see Section 10.4).
- If a patient never used the ABS eMDPI during the study or download of a given ABS eMDPI device was not successful, study day and weekly inhalational flow values will be missing. If download of a given wrist or ankle accelerometer was not successful, TDS and SDI indices will be missing. These missing data will not be imputed.
- In the derivation of Study Day X Inhalation flow values, if there was no albuterol use on Study Day X , then the closest preceding nonmissing Study Day Inhalation' is used as the 'Study Day X Inhalation' and the inhalational flow values for Study Day X are assigned accordingly (see Section 7.2.1).
- For patients in the ankle accelerometry analysis set if no step data are available for study day 1 through study day 14, the 'baseline TDS' is the first available TDS after study day 14 (see Section 4.2.4).
- For patients in the wrist accelerometry analysis set if no sleep parameter data are available for study day 1 through study day 14, the 'baseline value of a given sleep parameter' is the first available valid sleep parameter value after study day 14 (see Section 4.2.5).

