4.2.3. Inhalational Flow Values

The baseline inspiratory flow values are computed using the set of inhalations taken by the patient during study day 1 through day 14. Among these inhalations, the inhalation with the highest maximal inhalation flow (MIF) value is considered the ‘baseline inhalation’. The baseline MIF, inhalational volume, inhalation duration, and time to MIF values are those of the identified ‘baseline inhalation’. If no inhalations were taken during study day 1 through study day 14, the ‘baseline inhalation’ is the first available inhalation after study day 14.

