7.2. Inhalational Flow Values

7.2.1. Inhalational Flow Values Definitions

Study Day X and Week Y inhalational flow values are defined as follows:

Study Day X Inhalational Flow Values: The inhalational flow values for Study Day X are computed using the set of inhalations taken by the patient on Study Day X . Among these inhalations, the inhalation with the highest MIF value is considered the 'Study Day X Inhalation'. The Study Day X MIF, inhalational volume, inhalation duration, and time to MIF values are those of the identified 'Study Day X Inhalation'. If there was no albuterol use on Study Day X ,

then the closest preceding nonmissing Study Day Inhalation' is used as the 'Study Day *X* Inhalation' and the inhalational flow values for Study Day *X* are assigned accordingly.

Week *Y* Inhalational Flow Values: The inhalational flow values for Week *Y* are computed using the set of inhalations taken by the patient during a given week on the study. Among these inhalations, the inhalation with the highest MIF inhalation flow value is considered the 'Weekly *Y* Inhalation'. The Weekly *Y* MIF, inhalational volume, inhalation duration, and time to MIF values are those of the identified 'Weekly *Y* Inhalation'.

Note, if a patient never used the ABS eMDPI during the study or download of a given ABS eMDPI device was not successful, study day and weekly inhalational flow values will be missing.

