7.2.2. Analysis Methods for Inhalational Flow Values

7.2.2.1. Actual and Change from Baseline in Study Day *X* Inhalational Flow Values Prior to the Peak of a CAE

Among patients who experienced a CAE, summary descriptive statistics of the actual inhalational flow values and change from baseline in daily inhalational flow values for MIF, inhalational volume, inhalation duration, and time to MIF at 1 day (eg, the 24-hour period on the day prior to the date of the CAE symptom peak) and at 3, 5, 7, 10, 14, and 21 days preceding the peak of a CAE will be presented for all CAEs and by moderate CAEs and severe CAEs.

In this analysis, among patients experiencing more than 1 CAE, the subsequent CAEs can be considered a separate CAE distinct from the first (preceding) CAE provided the patient exhibited at least 1 day of baseline albuterol use after the first (preceding) CAE's date of symptom peak and prior to the subsequent CAE's date of symptom peak. For patients who experience multiple CAEs (eg, 3), for a given number of days preceding a CAE (eg, 7 days), if the (eg, third) CAE overlaps with the time period of the preceding (eg, second) CAE, the CAE (eg, third CAE) should not be included in the analysis.

Summary descriptive statistics of the actual inhalational flow values and change from baseline in daily inhalational flow values for MIF, inhalational volume, inhalation duration, and time to MIF will be presented for the first occurrence of a single day's albuterol use exceeding (i) 4 inhalations, (ii) 12 inhalations, and (iii) 20 inhalations, overall and by CAE status and by CAE severity.

In addition, summary descriptive statistics of the maximum change from baseline in daily inhalational flow values for MIF, inhalational volume, inhalation duration, and time to MIF will be presented overall and by CAE status and by CAE severity.

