7.5.2.1. Within Patient CAE Analyses

For each CAE event occurring at least 2 weeks after baseline, device-use measures (albuterol use, inhalational flow [MIF], inhalational volume, and time to MIF) will be summarized for each of 2 weeks of interest: first- 'CAE-adjacent week', the week immediately preceding the onset of CAE symptom (ie, day 1 through 7 preceding the date of the CAE symptom onset), and second – 'CAE-Prior Adjacent week', the week preceding that week (ie, during day 8 through 14 preceding the date of the CAE symptom onset). Summary measures of daily and or weekly use will be compared between the two weeks, as proposed below:

Albuterol use measures:

- total number of inhalations in that week
- the maximal daily number of inhalations in that week
- the mean number of daily inhalations (ie, total number of inhalations divided by number of days with number>0)
- occurrence of a single day's albuterol use exceeding 4 inhalations;
- occurrence of a single day's albuterol use exceeding 8 inhalations
- occurrence of a single day's albuterol use exceeding 12 inhalations
- number of days when albuterol use exceeding 4 inhalations;
- number of days when albuterol use exceeding 8 inhalations
- number of days when albuterol use exceeding 12 inhalations

To note, in this analysis, no inhalation in any day will be taken as a 0 count.

Inhalation flow values parameters:

- maximal daily MIF during the week
- minimal daily time to MIF within a week
- maximal total daily inhalational volume within a week,

To note, if no inhalation was taken at a specific day, flow value parameters will be missing and will not be imputed.

Analysis will be based on all patients CAEs for which there are 14 days (or more) prior to the CAE onset, where patient has been on study and CAE free.

Descriptive statistics of use measures in the 'CAE-adjacent week' and 'CAE-Prior Adjacent week' will be presented.

Continuous measures will be compared between the 2 weeks using paired t-test (and Wilcoxon Signed Ranks test) whereas binary patterns will be compared using Mc-Nemar test.

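### Daily flow values are carried forward without a maximum gap over no-use days, so the descriptive pre-exacerbation flow table can misdate values and overstate how many patients have data

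*SAP*

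**What the plan says.** SAP 7.2.1 takes a day's flow values from that day's inhalation with the highest maximal inhalational flow (MIF). For a day without albuterol use it states: "then the closest preceding nonmissing Study Day Inhalation' is used as the 'Study Day *X* Inhalation". SAP 4.6 gives the same rule for such a day: "then the closest preceding nonmissing Study Day Inhalation" supplies the values. Neither section limits how far back the carried value may lie, and neither asks for carried values to be marked or counted. Flow stays missing if the patient never used the device or its download failed.

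The daily values feed SAP 7.2.2.1, which plans "summary descriptive statistics of the actual inhalational flow values and change from baseline in daily inhalational flow values" at 1 day and "at 3, 5, 7, 10, 14, and 21 days preceding the peak of a CAE will be presented". This is description only; no test is attached.

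Other parts of the plan carry nothing forward:

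- SAP 7.5.2.1, which compares flow between the two weeks before symptom onset: "if no inhalation was taken at a specific day, flow value parameters will be missing and will not be imputed".
- Weekly flow values (SAP 7.2.1): they "are computed using the set of inhalations taken by the patient during a given week on the study".
- Daily steps and sleep measures (SAP 7.3.1 and 7.4.1): the value for a day is the one recorded on that day.

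Protocol 9.3 allows imputation where the SAP specifies it, so the rule is permitted. SAP 8 plans no sensitivity analysis.

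**The concern.** The purpose of the 7.2.2.1 table is timing. Protocol 2.1.1 uses inspiratory flow in place of peak expiratory flow. Protocol 3.3 cites a study in which changes appeared up to 10 days before an exacerbation and were well established by day 5. A figure labelled day -5 that was measured on day -12 cannot help to locate such a change.

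Three things can follow from the rule as written:

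- Values from before a decline stand in for values during it, so the decline looks smaller or later.
- If the carried inhalation is the baseline inhalation itself, the change from baseline is exactly zero.
- The count at each time point includes patients with no measurement that day.

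There is also an edge case. SAP 7.2.2.1 drops a later CAE whose look-back overlaps the preceding one. Carry-forward can reach past the start of the look-back, so a no-use day -21 could take a value from the earlier CAE without triggering that exclusion.

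**Working it through.** The documents state no share of no-use days, no typical gap and no expected fall in flow. There is no plan figure to reproduce, and the size has to be shown over a range.

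**Age of the values.** Let p be the daily probability of use, assumed constant and independent of flow. The share of values carried is 1 - p, the mean age of a carried value is 1/p days, and the share of all values at least 7 days old is (1 - p)^7.

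**Effect at day -1.** Assume a decline that builds linearly over the last 7 days, so that day -j shows (8 - j)/7 of it. The expected share displayed at day -1 is the sum over j = 1 to 7 of p(1 - p)^(j-1) × (8 - j)/7.

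For p = 0.4 this is 0.400 + 0.206 + 0.103 + 0.049 + 0.022 + 0.009 + 0.003 = 0.79.

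| Use days (p) | Values carried | Mean age if carried | At least 7 days old | Decline shown at day -1 |
|---|---|---|---|---|
| 20% | 80% | 5 days | 21% | 55% |
| 40% | 60% | 2.5 days | 2.8% | 79% |
| 60% | 40% | 1.7 days | 0.2% | 90% |
| 80% | 20% | 1.25 days | <0.1% | 96% |

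**Effect earlier in the window.** Take instead an assumed 10-unit linear fall from day -10 to day -1. The expected displayed value at day -t is the sum over ages a of p(1 - p)^a × true value at day -(t + a).

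| p | Day -1 (true 10.0) | Day -7 (true 3.33) |
|---|---|---|
| 0.3 | 7.51 (75%) | 1.63 (49%) |
| 0.5 | 8.89 (89%) | 2.36 (71%) |
| 0.8 | 9.72 (97%) | 3.06 (92%) |
| 0.95 | 9.94 (99%) | 3.27 (98%) |

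The proportional loss is larger near the start of the decline, which is where the table is meant to show timing.

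**Effect if use rises.** Keep the 7-day decline, with p = 0.4 until day -4 and p = 0.8 on days -3 to -1. Day -1 then shows 0.8 + 0.2 × 0.8 × 6/7 + 0.04 × 0.8 × 5/7 = 0.960 from the last three days. Days -4 to -7 add 0.008 × 0.4 × (4/7 + 0.6 × 3/7 + 0.36 × 2/7 + 0.216 × 1/7) = 0.003. The total is 96%, against 79% without the rise.

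**How common no-use days could be.** Protocol 3.3 gives 5.5 ± 9.7 actuations per day for the exacerbating group of a cited cohort.

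- If all patients used at the same Poisson rate, the no-use share is exp(-5.5) = 0.4%.
- If the SD is read as spread between patients (gamma-Poisson, an assumption), it is (1 + 9.7²/5.5)^(-5.5²/9.7²) = 39%. The probability of 7 straight no-use days is (1 + 7 × 9.7²/5.5)^(-5.5²/9.7²) = 21%.

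These two readings are far apart, so the documents cannot settle the size.

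**The case against.** The strongest reply has four parts.

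*The reach is narrow.* The tested comparison in 7.5.2.1 does not impute. Weekly values use only that week's inhalations. Summaries at the first day above 4, 12 or 20 inhalations fall on use days by definition, and repeating a value cannot alter a maximum change over the same days. All of this stands, and it limits the point to one descriptive table.

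*Low use shares are unfavourable inputs.* Patients enter uncontrolled, with an ACQ-5 score of at least 1.5 and a recent severe CAE, and the plan's hypothesis is that use rises before a severe CAE. This also stands. At 60% to 80% use days the loss at day -1 is 10% or less, and rising use reduces it further. It does not remove the problem at earlier time points or in patients who rarely use the inhaler.

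*The direction is not fixed.* A low value from a bad day can be carried over later no-use days. Separately, SAP 4.2.3 sets baseline from days 1 to 14: "Among these inhalations, the inhalation with the highest maximal inhalation flow (MIF) value is considered the" baseline inhalation. Comparing one day's maximum with a maximum over up to 14 days pushes the change towards a fall. In a simulation with no true decline and an assumed within-patient SD of 6 units, the mean change was about -5 to -8 units with or without carry-forward. That is a real opposing bias.

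*Leaving days missing has its own bias.* Flow is measured only when rescue is taken, so observed-only values describe use days, and the patients contributing may differ between day -21 and day -1. This stands, and is why the fix needs counts and a plain label.

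**Conclusion.** The point holds as a minor one. Followed as written, the rule lets the 7.2.2.1 table present old flow values as the value for a given pre-CAE day, unmarked, and counts those patients as having data. It can mute, delay or misdate a change. Under the assumptions shown, day -1 keeps about 55% to 96% of a 7-day linear decline as the share of use days goes from 20% to 80%. Those figures rest on a constant chance of use, independence of use and flow, and a linear decline; none of these comes from the documents.

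A reader might infer that the rule hides a decline. The documents do not support that: in every case worked above part of the decline remains, and the size and even the direction of the net error depend on quantities that the plan does not give.

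A reader might also infer that 7.2.2.1 and 7.5.2.1 report the same days with conflicting numbers. They are different summaries. The first takes single days counted back from symptom peak; the second takes weekly extremes counted back from symptom onset, for CAEs with at least 14 prior CAE-free days on study. They would differ even under one missing-data rule. What remains is an unexplained difference in how no-use days are handled.

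**What to change.** In SAP 4.6 and 7.2.1, replace the carry-forward rule with the one in 7.5.2.1, so that daily flow is missing on a day without an inhalation. In the 7.2.2.1 table, show at each time point the number of CAEs and of patients with an actual inhalation, and state that the values describe use days only.

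If a carried-forward version is wanted, make it supplementary. Set a maximum gap that does not reach back into an earlier CAE, and report the number and age of the carried values at each time point.

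The cost is SAP wording and programming, with no new data. There will be fewer patients per time point, and the mix of patients can vary from one time point to the next; the counts make that visible.

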5. STUDY POPULATION

5.1. General

The ITT analysis set will be used for all study population summaries unless otherwise specified. The data will be listed for all patients enrolled into the database.

5.2. Patient Disposition

Data from patients screened; patients who were screen failures; patients who re-screened; patients screened but not enrolled and reason for non-enrollment; patients who are enrolled; patients enrolled but who do not use ABS eMDPI at least once; patients in the ITT analysis set; patients in the ankle accelerometry cohort and patients in the wrist accelerometry cohort; patients who complete the study; and patients who withdraw from the study and the reason for withdrawal will be summarized using descriptive summary statistics (n, %) for all patients entered into the database.

5.3. Demographics and Baseline Characteristics

Patient demographic and baseline characteristics will be summarized using descriptive statistics. Demographic and baseline characteristics will include: age, sex, race, ethnicity, weight, height, and body mass index (BMI), vital signs, TDS, inhalational flow values and sleep disruption indices.

The formula for BMI is: $BMI = \frac{\text{weight}}{\text{height}^2}$,

where weight is in kilograms (kg), height in meters (m) and BMI is kg/m².

Baseline inhalational flow values include MIF, inhalational volume, inhalation duration, and time to MIF. Baseline sleep disruption indices include nighttime average total time in bed, nighttime average total sleep time, nighttime average sleep latency time, nighttime average waking after sleep onset, total time awake at night, daytime average minutes asleep, longest daytime sleep episode and longest nighttime wake episode.

Demographics and baseline characteristics will be summarized by analysis set (ITT analysis set and the ankle and wrist accelerometry analysis sets).

5.4. Medical History

All medical history will be coded using the most current version of the Medical Dictionary for Regulatory Activities (MedDRA) at the time of database lock. The incidence of medical history abnormalities will be summarized using descriptive statistics by system organ class (SOC) and preferred term (PT). Patients are counted only once in each preferred term and SOC category even if they have multiple applicable findings.

Summaries will be provided for the ITT analysis set and the ankle and wrist accelerometry analysis sets.

5.5. Asthma History

Asthma history data will be summarized. This will include duration of asthma, history of positive methacholine challenge within the past 5 years, greater than 20% variability in FEV1 between 2 prior measurements, and diurnal variation in peak flow measurement reversibility and/or with an Asthma Control Questionnaire (ASQ) score of at least 1.5.

Summaries will be provided for the ITT analysis set and the ankle and wrist accelerometry analysis sets.

5.6. Asthma Exacerbations History

Asthma exacerbations history data will be summarized. This will include asthma exacerbations in the past 12 months, hospitalizations, emergency room visits, urgent care, doctor visits for asthma exacerbations, and systemic steroids administration for asthma.

Summaries will be provided for the ITT analysis set and the ankle and wrist accelerometry analysis sets.

5.7. Prior Therapy and Medication

All prior medications will be coded using the most current version of the World Health Organization drug dictionary (WHO Drug) at the time of database lock. The incidence of prior medications will be summarized using descriptive statistics (count and percentages) by therapeutic class and PT. In addition, a summary table of the incidence of prior asthma medications will be provided. Patients are counted only once in each therapeutic class category, and only once in each PT category. Prior medications will include medications taken within 30 days prior to the first day that IMP is dispensed.

Summaries will be provided for the ITT analysis set and the ankle and wrist accelerometry analysis sets.

5.8. Childbearing Potential and Methods of Contraception

Information related to childbearing potential, contraception, and menopause will be collected at Screening and at the Final/Early Termination visit. All information for childbearing potential will be provided in a listing by patient.

5.9. Study Protocol Violations

Data from patients with any protocol violation during the study will be summarized overall and for each category using descriptive statistics. Of note, medication errors, overdose, misuse, abuse, off-label use, and occupational exposure will be summarized in category. Protocol violations also include nonadherence on the part of the patient, the investigator, or the sponsor to protocol-specific inclusion/exclusion criteria, primary outcome measure criteria, or GCP guidelines; use of prohibited medications; or any other deviations that may have an impact on the processes put in place for the care and safety of the patients. Protocol violations will be reviewed and major protocol violations will be identified and confirmed by the clinical and statistical personnel prior to database lock. Major violations are violations that could have an effect on the primary outcome.

Patient with at least 1 protocol violation for each category will be summarized using count and percentages by analysis set (ITT analysis set, and the ankle and wrist accelerometry analysis sets).

5.10. eMDPI Time on Study; Days and Weeks

Summary statistics of the eMDPI time on study in study in days and weeks (days divided by 7) will be presented overall and by CAE status and by CAE severity for the ITT analysis set, ankle accelerometry analysis set and the wrist accelerometry analysis set.

6. EFFICACY ANALYSIS

Efficacy will not be assessed in this study. Endpoint analyses are described in Section [7](#).

7. ENDPOINT ANALYSES

All endpoint analyses will be performed using the ITT analysis set.

Data listings will be presented by patient.

7.1. eMDPI: Albuterol Use

7.1.1. Albuterol Use Definition

Baseline albuterol use is defined as no more than 4 inhalations (eg, 0 to 4 inhalations) per day of use regardless of the number of days albuterol is used in a 7-day period.

Daily baseline albuterol use is defined as no more than 4 inhalations (eg, 0 to 4 inhalations) per day.

Week 1 Patient Albuterol Use: Week 1 patient albuterol use is each patient's total number of albuterol inhalations taken and the number of days used during the first week (study day 1 through study day 7) of study participation with an indicator of whether or not any daily usage of albuterol exceeded 4 inhalations. It is presented as WK1:I#iD#dMT4Y/N, where "i" is the number of albuterol inhalations and "d" is the number of days used in the first 7 days of the study, and "MT4Y/N" is an indicator of whether or not any of the days albuterol was used exceeded 4 inhalations. For example, "I28D7MT4N" indicates a total of 28 inhalations were taken, albuterol use was used each day and none of the daily number of inhalations exceeded 4 (No More Than 4 inhalations per day Yes/ No).

Week 2 Patient Albuterol Use: Week 2 patient albuterol use is each patient's total number of albuterol inhalations taken and the number days used during the second week (study day 8 through study day 14) of study participation with an indicator of whether or not any daily usage of albuterol exceeded 4 inhalations. It is presented as "WK2:I#iD#dMT4Y/N", where "i" is the number of albuterol inhalations and "d" is the number of days used in the second week of study.

Albuterol use will be examined by the following 3 parameters; (i) total number of inhalations in the days preceding the peak of a CAE, (ii) number of days prior to the peak of a CAE when albuterol use increased, and (iii) number of albuterol uses in the day preceding a CAE.

The maximum number of inhalations taken within a 24-hour period by each patient: The date and time stamp of the inhalations are taken into consideration when determining the maximum number of inhalations taken within a 24-hour period by each patient. For patients who experienced a CAE, the maximum number of inhalations taken within a 24-hour period is determined among the days prior to the date of the symptom peak of the exacerbation.

